6.2.7.2. Definition of an SAE

An SAE is any untoward medical occurrence that, at any dose:

- a. Results in death
- b. Is life threatening

NOTE: The term “life threatening” in the definition of “serious” refers to an event in which the subject was at risk of death at the time of the event. It does not refer to an event, which hypothetically might have caused death, if it were more severe.

- c. Requires hospitalization or prolongation of existing hospitalization

NOTE: In general, hospitalization signifies that the subject has been detained (usually involving at least an overnight stay) at the hospital or emergency ward for observation and/or treatment that would not have been appropriate in the physician's office or out-patient setting. Complications that occur during hospitalization are AEs. If a complication prolongs hospitalization or fulfills any other serious criteria, the event is serious. When in doubt as to whether “hospitalization” occurred or was necessary, the AE should be considered serious.

Hospitalization for elective treatment of a pre-existing condition that did not worsen from Baseline is not considered an AE.

- d. Results in disability/incapacity, or

NOTE: The term disability means a substantial disruption of a person's ability to conduct normal life functions. This definition is not intended to include experiences of relatively minor medical significance such as uncomplicated headache, nausea, vomiting, diarrhea, influenza, and accidental trauma (e.g., sprained ankle) which may interfere or prevent everyday life functions but do not constitute a substantial disruption.

- e. Is a congenital anomaly/birth defect

- f. Medical or scientific judgment should be exercised in deciding whether reporting is appropriate in other situations, such as important medical events that may not be immediately life threatening or result in death or hospitalization but may jeopardize the subject or may require medical or surgical intervention to prevent 1 of the other

outcomes listed in the aforementioned definition. These should also be considered serious. Examples of such events are invasive or malignant cancers, intensive treatment in an emergency room or at home for allergic bronchospasm, blood dyscrasias or convulsions that do not result in hospitalization, or development of drug dependency or drug abuse.

6.2.8. Laboratory and Other Safety Assessment Abnormalities Reported as SAEs

Any abnormal laboratory test results (hematology, clinical chemistry, or urinalysis) or other safety assessments (e.g., electrocardiograms, radiological scans, vital sign measurements), including those that worsen from Baseline, felt to be clinically significant in the medical and scientific judgment of the RCC-PI are to be recorded as SAEs. However, any clinically significant safety assessments that are associated with the underlying disease, unless judged by the RCC-PI to be more severe than expected for the subject's condition, are **not** to be reported as SAEs.

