6.2.7. Adverse Events

The RCC-PI or RCC site staff will be responsible for detecting, documenting, and reporting events that meet the definition of an SAE. Nonserious AEs will not be tracked.

The outcomes for this study may represent a number of potential adverse drug experiences or events that include but may not be limited to the following:

- Reports of child hospitalizations (see Section [6.3](#))
- Reports of chronic health conditions in the child (see Section [6.2.2](#))
- Reports of congenital anomalies in the child (see Section [6.2.3](#))
- Reports of child death (see Section [6.2.4](#))
- Reports of developmental delays in the child (see Section [6.2.5.2](#))
- Reports of any other SAEs in the child (see Section [6.2.7.2](#))

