6.2.7.1. Definition of an AE

Any untoward medical occurrence in a patient or clinical investigation subject, temporally associated with the use of a medicinal product, whether or not considered related to the medicinal product.

Note: An AE can therefore be any unfavorable and unintended sign (including an abnormal laboratory finding), symptom, or disease (new or exacerbated) temporally associated with the use of a medicinal product.

Events meeting the definition of an AE include:

- Exacerbation of a chronic or intermittent pre-existing condition including either an increase in frequency and/or intensity of the condition
- New conditions detected or diagnosed after study treatment administration even though it may have been present prior to the start of the study
- Signs, symptoms, or the clinical sequelae of a suspected interaction
- Signs, symptoms, or the clinical sequelae of a suspected overdose of either study treatment or a concomitant medication (overdose per se will not be reported as an AE/SAE) unless this is an intentional overdose taken with possible suicidal/self-harming intent. This should be reported regardless of sequelae.

Events that **do not** meet the definition of an AE include:

- Medical or surgical procedure (e.g., endoscopy, appendectomy); the condition that leads to the procedure is an AE
- Situations where an untoward medical occurrence did not occur (social and/or convenience admission to a hospital)
- Anticipated day-to-day fluctuations of pre-existing disease(s) or condition(s) present or detected at the start of the study that do not worsen
- The disease/disorder being studied, or expected progression, signs, or symptoms of the disease/disorder being studied, unless more severe than expected for the subject's condition

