6.2.11. Time Period and Frequency of Detecting SAEs

The RCC-PI or RCC site staff is responsible for detecting, documenting, and reporting events that meet the definition of an SAE.

Child SAEs will be collected from after 28 days post EDD until 24 months chronological age. All SAEs will be reported to GSK/PPD within 24 hours, as indicated in Section [6.2.12](#).

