6.2.14. Prompt Reporting of SAEs and Other Events to GSK/PPD

Serious AEs meeting predefined criteria will be reported promptly by the RCC-PI to GSK, as described in the following table, once the RCC-PI determines that the event meets the protocol definition for that event.

		Initial Reports		Follow-Up Information on a Previous Report	
Type of Event	Time Frame	Documents	Time Frame	Documents	
All SAEs	24 hours	“SAE” data collection tool	24 hours	Updated “SAE” data collection tool	
Cardiovascular or death event	Initial and follow-up reports to be completed within 1 week of when the cardiovascular event or death is reported	“CV events” and/or “death” data collection tool(s), if applicable	Initial and follow-up reports to be completed within 1 week of when the cardiovascular event or death is reported	Updated “CV events” and/or “death” data collection tool(s), if applicable	

CV = cardiovascular; SAE = serious adverse event.

The contact information for reporting SAEs is as follows:

Issue	North America Contract	Latin America Contact	Europe/Asia Contact
Serious Adverse Event Reporting	24-Hour Safety Hotline: PPD [REDACTED] Safety Fax: PPD [REDACTED]	24-Hour Safety Hotline: PPD [REDACTED] Safety Fax: PPD [REDACTED]	24-Hour Safety Hotline: PPD [REDACTED] Safety Fax: PPD [REDACTED]

The method of recording, evaluating, and following up of SAEs including procedures for completing and transmitting SAE reports to GSK are provided in the SPM. Procedures for poststudy SAEs are provided in the SPM.

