### 7.2.2.1. Serious Adverse Events

SAEs will be coded using the Medical Dictionary for Regulatory Activities (MedDRA) coding dictionary. A mapping of the MedDRA primary system organ class (SOC) and preferred term (PT) that each verbatim term has been coded to will be provided in a listing. In general, SAEs will be presented in descending order from the SOC with the highest total incidence (that is, summed across all treatment groups) for any adverse event within the class to the SOC with the lowest total incidence. Within the SOC level, SAEs will be presented in descending order from the PT with the highest total incidence to the PT with the lowest total incidence. If the total incidence for any two or more PTs within an SOC is equal, the PTs will be presented in alphabetical order. A PT will not be presented if no adverse events occur within the level. At each level of summarization, a subject is counted only once if the subject reported one or more events.

The seriousness of an AE should be assessed by the Investigator independently from the severity of the AE. An SAE is defined as any untoward medical occurrence that at any dose results in death, is life-threatening, requires hospitalization or prolongation of existing hospitalization, results in disability/incapacity, or is a congenital anomaly/birth defect.

Important medical events that may not result in death, be life-threatening, or require hospitalization may be considered SAEs when, based upon medical judgment, they may jeopardize the subject and may require medical or surgical intervention to prevent one of the outcomes listed above.

The number and percentage of subjects with any SAEs occurred before subjects reach 24 months chronological age will be summarized by treatment group in the tables. Within each group, SAEs will be summarized by frequency and proportion of total subjects, by event type, and by category of body system. A listing of SAEs will be provided.

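### Protocol 6.2.8 lets clinical significance alone make an abnormal finding an SAE, in conflict with 6.2.7.2 and SAP 7.2.2.1, and could add nonserious findings to Tables 10.5 and 20.5

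*Protocol*

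**What the plan says.** Protocol 6.2.8 covers abnormal laboratory tests and other safety assessments such as electrocardiograms, scans and vital signs. Those "felt to be clinically significant in the medical and scientific judgment of the RCC-PI are to be recorded as SAEs". Its next sentence makes an exception and keeps out of SAE reporting "any clinically significant safety assessments that are associated with the underlying disease, unless judged by the RCC-PI to be more severe than expected". The protocol does not define the underlying disease for this cohort.

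The rest of the plan uses a seriousness definition:

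- Protocol 6.2.7.1 counts "any unfavorable and unintended sign (including an abnormal laboratory finding") as a possible AE, which leaves seriousness as a separate step.
- Protocol 6.2.7.2 begins "An SAE is any untoward medical occurrence that, at any dose" and lists criteria a to f: death, threat to life, hospitalization, disability, congenital anomaly, and important medical events by judgment.
- Protocol 6.2.11 makes the RCC-PI or site staff "responsible for detecting, documenting, and reporting events that meet the definition of an SAE".
- Protocol 6.2.14 starts the reporting clock "once the RCC-PI determines that the event meets the protocol definition for that event".
- Protocol 8.3.5.1.2 bases the SAE summaries on 6.2.7.2 and does not mention 6.2.8.
- SAP 7.2.2.1 repeats the seriousness definition with no clinical-significance route.

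On nonserious events, Protocol 6.2.7 says "Nonserious AEs will not be tracked". For the tables, SAP 7.2.2.1 reports the number and percentage of children with any SAE before 24 months chronological age, and within each group "SAEs will be summarized by frequency and proportion of total subjects, by event type, and by category of body system". It states no filter on which criterion an SAE met.

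**The concern.** A finding can be clinically significant without meeting any seriousness criterion. Under 6.2.8 it is recorded as an SAE. Under 6.2.7.2, 6.2.11, 6.2.14, 8.3.5.1.2 and SAP 7.2.2.1 it is not one. An RCC-PI who follows the protocol literally cannot satisfy both sets of sections, and a programmer working from the SAP has no rule for the records that result.

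No nonserious AE table exists to hold such findings, so if they are recorded at all they are recorded as SAEs. Whether a finding is recorded would depend on how many medical records a child generates, on each regional RCC-PI's threshold for clinical significance, and on how that RCC-PI reads the exemption. The underlying disease could be taken as prematurity, as the child's own pre-existing condition, or as nothing, because eligibility rests on the mother having been dosed and there are no exclusion criteria.

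What is at stake is how the SAE summaries read in a 98-child descriptive study, where one child can visibly move a percentage. Nonserious entries occurring equally in all groups would also dilute a real difference.

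**Working it through.** **No figure to reproduce.** The documents give no SAE rate, no count of 6.2.8-only records and no power calculation that bears on this point. The check is a comparison of text plus two sensitivity calculations.

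**Step 1: follow one finding through the plan.** Take an abnormal result that the RCC-PI judges clinically significant, that meets none of criteria a to f, and that falls outside the exemption.

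| Section | Treatment |
|---|---|
| Protocol 6.2.8 | Recorded as an SAE |
| Protocol 6.2.7.1 and 6.2.7.2 | An AE, not serious |
| Protocol 6.2.7 | Not tracked |
| Protocol 6.2.11 and 6.2.14 | Not reportable |
| Protocol 8.3.5.1.2 | Outside the SAE summaries |
| SAP 7.2.2.1, definition | Not an SAE |
| SAP 7.2.2.1, tabulation | Counted if it is in the SAE dataset, since no filter is stated |

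**Step 2: can such findings arise?** No laboratory tests are scheduled (Protocol 6.2.15.1), and SAEs come mainly from the parent-completed questionnaire (6.2.12). The RCC-PI does obtain records for hospitalizations and for surgeries other than simple routine outpatient procedures, and obtains emergency or urgent care records when the indication suggests a true emergency (Confirmation of Parent-Reported Data, under 6.2.1.1). Such records can contain the results that 6.2.8 names.

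**Step 3: where would they show?** SAP 7.2.2.1 counts a child once at each level of summarization. A hospitalized child will generally already count under criterion c, so a 6.2.8-only record would rarely change the any-SAE row for that child but could add to an organ class or preferred term row. The any-SAE row itself would move mainly through children who were not hospitalized.

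**Step 4: effect of one extra child, 100/n.**

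Table 20.5 uses the ARIOS Safety population. Enrolled numbers come from the Amendment 02 justification in Protocol Appendix 1: placebo 6, atosiban 43, retosiban 49, and 6 + 43 + 49 = 98.

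Table 10.5 uses the Infant Safety population, whose size by group is not stated. I assume the trial group sizes in Protocol 1.1.1: retosiban 10 + 50 = 60, atosiban 47, placebo 13.

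| Group | Table 20.5 | Table 10.5 (assumed n) |
|---|---|---|
| Retosiban | 100/49 = 2.0 points | 100/60 = 1.7 points |
| Atosiban | 100/43 = 2.3 points | 100/47 = 2.1 points |
| Placebo | 100/6 = 16.7 points | 100/13 = 7.7 points |
| All comparators | 100/49 = 2.0 points | 100/60 = 1.7 points |

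**Step 5: direction if such records occur equally in both groups.** Let p be the true SAE risk and q the share of the other children who are recorded only through 6.2.8. The observed risk is p + (1 − p)q. The values below are illustrative assumptions: p = 20% in one group and 10% in the other, a true ratio of 2.0.

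| q | First group | Second group | Ratio |
|---|---|---|---|
| 0% | 20.0% | 10.0% | 2.00 |
| 2% | 0.20 + 0.80 × 0.02 = 21.6% | 0.10 + 0.90 × 0.02 = 11.8% | 1.83 |
| 5% | 24.0% | 14.5% | 1.66 |
| 10% | 28.0% | 19.0% | 1.47 |

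If q is above zero and the records stay in the table, both percentages rise and the ratio moves toward 1. If q is zero, nothing changes.

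**The case against.** A reader might infer that 6.2.8 turns every clinically significant abnormality into an SAE and so inflates the main SAE table. The documents do not support either part. The second sentence of 6.2.8 exempts findings associated with the underlying disease unless they are more severe than expected. Inflation is only a possibility, because 8.3.5.1.2 ties the summaries to 6.2.7.2, the SAP uses the same definition, and no count of such records is given.

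A reader might also infer that the exemption is meaningless here, or that Tables 10.5 and 20.5 carry the safety conclusion. Neither follows. Children born after preterm labor can have pre-existing conditions, so the exemption is undefined rather than empty. SAE incidence is not a listed primary endpoint. Chronic conditions, neurodevelopment and congenital anomalies have their own tables, deaths have a listing, and Listing 42 shows the SAEs of enrolled children individually.

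Three further points on the other side have weight. Criterion f in 6.2.7.2 already admits medical judgment and gives blood dyscrasias as an example, so part of what 6.2.8 captures is serious anyway. The RCC-PIs are blinded (Protocol 5.3), and no directional bias is shown. Broad capture is also a defensible cautious choice when nonserious events are not tracked.

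These points reduce the importance but leave the conflict in place. Criterion f covers events that may jeopardize the child or need intervention to prevent a serious outcome, which is narrower than clinical significance. If broad capture is intended, the analysis section and the SAP should say so, and at present both use the narrower definition.

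**Conclusion.** The point holds as an internal conflict of low priority. Section 6.2.8 sets a recording rule that the protocol's own definition, reporting and analysis sections and the SAP do not share, and the SAP does not settle whether records made only under that rule are tabulated.

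The size is unknown. The one-child figures show how sensitive each percentage is; they do not estimate inflation. They are exact for Table 20.5 if all 98 enrolled infants form the denominators. For Table 10.5 they rest on the assumption that the group sizes in Protocol 1.1.1 are the Infant Safety denominators. The movement of the ratio toward 1 rests on equal q in the groups being compared and on the illustrative risks chosen.

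**What to change.** - **Protocol 6.2.8:** reword it so that an abnormal result or assessment is recorded as an SAE only when it meets a criterion in 6.2.7.2. One definition then governs recording, reporting and summaries. Define the underlying disease for this cohort or remove the exemption.
- **SAP 7.2.2.1:** state that Tables 10.5 and 20.5 count only events meeting a 6.2.7.2 criterion, and that records entered solely under 6.2.8 are flagged and shown separately.
- **Timing:** settle this before database freeze. The SAP synopsis places all decisions on the final analyses before that point, and SAP section 8 rules out changes after the blind is broken.

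The SAP step matters more than the protocol wording, because much of the follow-up is already done: 34 of 98 infants had completed 24 months at the June 2018 data cut. The cost is a small wording change in each document and one flag in the SAE dataset. If the criterion met was not captured, a small blinded review of the SAEs already recorded is also needed. No new data are required from families.

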6.2.9. Cardiovascular Events

The RCC-PI will be required to fill out event specific data collection tools for the following SAEs:

- Myocardial infarction/unstable angina
- Congestive heart failure
- Arrhythmias
- Valvulopathy
- Pulmonary hypertension
- Cerebrovascular events/stroke and transient ischemic attack
- Peripheral arterial thromboembolism
- Deep venous thrombosis/pulmonary embolism
- Revascularization

This information should be recorded in the specific cardiovascular eCRF within 1 week of when the SAE(s) are first reported.

6.2.10. Death Events

The proportion of deaths that occur after 28 days post EDD and up to 24 months chronological age will be collected.

In addition, all deaths will require a specific death data collection tool to be completed. The death data collection tool includes questions regarding cardiovascular (including sudden cardiac death) and noncardiovascular death.

This information should be recorded in the specific death eCRF within 1 week of when the death is first reported.

6.2.11. Time Period and Frequency of Detecting SAEs

The RCC-PI or RCC site staff is responsible for detecting, documenting, and reporting events that meet the definition of an SAE.

Child SAEs will be collected from after 28 days post EDD until 24 months chronological age. All SAEs will be reported to GSK/PPD within 24 hours, as indicated in Section [6.2.12](#).

6.2.12. Method of Detecting SAEs

Serious AEs will be primarily collected through the CHI questionnaire in an electronic device. Designated events and/or responses will be followed by the HCP as discussed in Section [6.2.7.2](#). Care must be taken not to introduce bias when detecting SAEs. If phone contact needs to be made with a parent/legal guardian by the RCC-PI, open-ended and nonleading verbal questioning of the subject is the preferred method to clarify reported SAEs.

6.2.13. Follow-up of SAEs

Any SAEs or AEs of special interest that were ongoing at the end of the Phase III treatment studies and any new SAEs reported during this study will be followed until resolution, until the condition stabilizes, until the event is otherwise explained, or until the subject is lost to follow-up.

6.2.14. Prompt Reporting of SAEs and Other Events to GSK/PPD

Serious AEs meeting predefined criteria will be reported promptly by the RCC-PI to GSK, as described in the following table, once the RCC-PI determines that the event meets the protocol definition for that event.

		Initial Reports		Follow-Up Information on a Previous Report	
Type of Event	Time Frame	Documents	Time Frame	Documents	
All SAEs	24 hours	“SAE” data collection tool	24 hours	Updated “SAE” data collection tool	
Cardiovascular or death event	Initial and follow-up reports to be completed within 1 week of when the cardiovascular event or death is reported	“CV events” and/or “death” data collection tool(s), if applicable	Initial and follow-up reports to be completed within 1 week of when the cardiovascular event or death is reported	Updated “CV events” and/or “death” data collection tool(s), if applicable	

CV = cardiovascular; SAE = serious adverse event.

The contact information for reporting SAEs is as follows:

Issue	North America Contract	Latin America Contact	Europe/Asia Contact
Serious Adverse Event Reporting	24-Hour Safety Hotline: PPD [REDACTED] Safety Fax: PPD [REDACTED]	24-Hour Safety Hotline: PPD [REDACTED] Safety Fax: PPD [REDACTED]	24-Hour Safety Hotline: PPD [REDACTED] Safety Fax: PPD [REDACTED]

The method of recording, evaluating, and following up of SAEs including procedures for completing and transmitting SAE reports to GSK are provided in the SPM. Procedures for poststudy SAEs are provided in the SPM.

6.2.14.1. Regulatory Reporting Requirements for SAEs

Prompt notification of SAEs by the RCC-PI to GSK is essential so that legal obligations and ethical responsibilities towards the safety of subjects are met.

GSK has a legal responsibility to notify both the local regulatory authority and other regulatory agencies about the safety of a product under clinical investigation. GSK will comply with country specific regulatory requirements relating to safety reporting to the regulatory authority, Institutional Review Board (IRB)/Independent Ethics Committee (IEC) and RCC-PIs.

The RCC-PI safety reports are prepared for suspected unexpected serious adverse reactions according to local regulatory requirements and GSK policy and are forwarded to other RCC-PIs as necessary.

The RCC-PI who receives a safety report describing an SAE(s) or other specific safety information (e.g., summary or listing of SAEs) from GSK will file it with the IB and will notify the IRB/IEC, if appropriate according to local requirements.

